7.2 Safety Population

The safety population will consist of all subjects treated with OTL-101 at UCLA/NIH (current study cohort) and the complete HSCT historical control cohort consisting of ADA-SCID patients with any type of donor treated with HSCT at either GOSH or Duke University from the year 2000 onwards.

8 Statistical Methods

In general, continuous variables will be summarised using the mean, standard deviation, median, minimum, maximum and number of subjects. Categorical variables will be summarised using number of subjects and percentages.

For all summaries, the HSCT controls will be summarised in the groups of those without a matched related donor, those with a matched related donor and all subjects.

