Busulfan has been widely used for myeloablation in bone marrow transplantation and has a well-described toxicity profile. When Busulfan is used at high doses (16 mg/kg, which translates to approximately 40 mg/m² x 16 doses) along with cyclophosphamide, as administered prior to allogeneic bone marrow transplantation, significant toxicity including thrombocytopenia and neutropenia have occurred, Busulfan-related seizures and emesis may occur and are largely preventable with prophylactic medication. Rarely, veno-occlusive disease and pulmonary fibrosis (the latter two toxicities seen with Busulfan/cyclophosphamide combinations) have been described. However, the nature and extent of toxicity resulting from low-dose Busulfan (e.g. 4 mg/kg IV x 1) in a pediatric population are not known. A recent report in ten ADA-SCID children demonstrated evidence of neutropenia but suggested no limiting toxicity with 4 mg/kg ([Aiuti, A et al., 2002, 2009](#)). These complications of high dose busulfan in combination with other chemotherapy drugs has not been seen in any of the more than 25 ADA-deficient patients treated using low dose busulfan.

Busulfan is mutagenic (a clastogenic agent, which induces DNA damage) and another potential cause for cancer in this study group. Although Busulfan is frequently used in combination with cyclophosphamide in the clinical setting, there is the risk that it independently can cause cancer, even with the low dose proposed in this study. Also, there is the possibility that a subject will be exposed to busulfan without receiving the gene-modified cells.

Insertional oncogenesis (IO):

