Back-up bone marrow: A backup bone marrow inoculum (5×10^7 nucleated cells/kg from whole marrow or 3×10^7 mononuclear cells from ficolled marrow) will be cryopreserved, and CD34+ cells will be isolated from the remainder.

Cell sufficiency criteria and resulting action: Once the CD34+ cells are isolated and counted, the number of CD34+ cells/kg is calculated.

1) If a sufficient number of cells ($\geq 1 \times 10^6$ /kg CD34+ cells) are isolated after the back-up was removed, the subject will receive busulfan (**See [Appendix C](#)**), the CD34+ cells will be transduced with the EFS-ADA lentiviral vector, and OTL-101 will be re-administered if they meet release criteria.

2) If less than 5×10^5 CD34+ cells/kg are isolated from the initial harvest, the subject would meet subject stopping criteria, would not receive busulfan, would be withdrawn from the study, would remain on PEG-ADA and would return to routine medical care.

3) If between $\geq 5 \times 10^5$ to $< 1 \times 10^6$ /kg CD34+ cells are isolated, the CD34+ cells will be cryopreserved as additional back-up and PEG-ADA will be continued.

The patient will be offered to return later for a second collection to isolate the cells for the transduction. If $> 1.0 \times 10^6$ CD34+ cells/kg are isolated from a second harvest (and adequate back-up had been cryopreserved from the first harvest), these cells will be transduced with the EFS-ADA lentiviral vector, the subject will receive busulfan, and OTL-101.

4) If OTL-101 fails to meet any one of the release criteria and the subject has received busulfan, the OTL-101 will not be given, the back-up cells will be administered, the subject would meet subject stopping criteria, and s/he would be withdrawn from the study, would remain on PEG-ADA and would return to routine medical care.

5) If $\leq 0.5 \times 10^6$ /kg cells are in OTL-101, which meets release criteria, OTL-101 will be administered and then the back-up cells will also be given within 1-2 days after OTL-101 has been given.

7.4 Post-treatment Phase:

Post-transplant care: Subjects will be kept in the hospital for close monitoring for at least 7 days post-infusion of the cells. However, they may be kept for a longer period as deemed clinically necessary, depending on medical care needed (e.g. CVC care, infections, protective isolation,

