9.12 Replacement of a Participant Who Discontinues Study Treatment

Subjects who discontinue study prior to infusion of gene-modified cells will be replaced. A total of 20 subjects will be enrolled.

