11.5 Analysis Sets

11.5.1 Safety Analysis Set

The safety analysis set will consist of all patients treated with OTL-101 at UCLA/NIH (current study cohort) and the complete HSCT historical control cohort, consisting of ADA-SCID subjects with any type of donor treated with HSCT at either GOSH/UCL (UK) or Duke University Children's Hospital (USA) from the year 2000 onward.

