11.5.2 Full Analysis Set

The full analysis set will consist of all patients treated with OTL-101 at UCLA/NIH (current study cohort).

The primary analysis set for efficacy from the HSCT historical control cohort will consist of ADA-SCID patients without a medically eligible HLA-matched sibling/family donor and treated with HSCT at either GOSH/UCL or Duke University Children's Hospital from the year 2000 onwards.

Additional efficacy comparisons will be made with:

- ADA-SCID patients with matched related donors treated with HSCT at either GOSH/UCL or Duke University Children's Hospital from the year 2000 onwards;
- the complete HSCT historical control cohort consisting of ADA-SCID patients with any type of donor treated with HSCT at either GOSH/UCL or Duke University Children's Hospital from the year 2000 onwards.

Note however that for the analysis of primary efficacy, full EFS data for HSCT subjects might only be available for the 12-month (primary) and 24-month (end of study) analyses.

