7.1 Efficacy Population

The primary efficacy population will consist of all patients treated with OTL-101 at UCLA/NIH (current study cohort).

The primary efficacy population from the HSCT historical control cohort will consist of ADA-SCID patients without a medically eligible HLA-matched sibling/family donor and treated with HSCT at either Great Ormond Street Hospital (GOSH) or Duke University from the year 2000 onwards.

Final Version 4.0 Page 11 of 27

Additional efficacy comparisons will be made with:

- ADA-SCID patients with matched related donors treated with HSCT at either GOSH or Duke University from the year 2000 onwards;
- the complete HSCT historical control cohort consisting of ADA-SCID patients with any type of donor treated with HSCT at either GOSH or Duke University from the year 2000 onwards.

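### A child given busulfan whose product then fails release enters no planned SAE, OS or EvFS rate, because every trial-arm analysis set requires OTL-101 infusion

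*SAP*

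**What the plan says.** SAP 7.2 defines the trial arm's safety set by receipt of the product: "The safety population will consist of all subjects treated with OTL-101 at UCLA/NIH". SAP 7.1 (efficacy population) and Protocol 11.5.1 and 11.5.2 (safety and full analysis sets) use the same condition. Neither document defines a set of enrolled, harvested or busulfan-exposed subjects for any analysis of outcomes.

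The protocol foresees conditioning without the product. Section 2.3.1 warns that "there is the possibility that a subject will be exposed to busulfan without receiving the gene-modified cells". Section 7.3, item 4 of the cell-sufficiency rules, sets the path: "If OTL-101 fails to meet any one of the release criteria and the subject has received busulfan, the OTL-101 will not be given". The child then gets the back-up cells, is withdrawn and stays on PEG-ADA. Section 9.10 removes participants for whom no adequate product can be made, and section 9.12 adds: "Subjects who discontinue study prior to infusion of gene-modified cells will be replaced".

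Two SAP rules bear on the same child. Under 8.4.1.1 an adverse event is treatment-emergent only from the start of the OTL-101 infusion. Under 8.4.1.2 the SAE incidence tables, which carry the primary safety endpoint, use treatment-emergent events only, and earlier SAEs are listed.

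**The concern.** The product is made individually for each child, and busulfan is given before it is known whether that product can be released. Exposure to conditioning without the product is therefore a possible harm of the treatment strategy. Protocol 2.3.1 itself calls busulfan mutagenic and a potential cause of cancer at the dose used. A safety set that starts at infusion cannot show that harm as a rate. An efficacy set that starts at infusion answers a narrower question, namely what happens once the product is in the child. With 20 subjects, one child more or less in the denominator visibly moves the estimate and its lower confidence limit.

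**Working it through.** **Sequence of events.** Protocol 8.3 places busulfan about 12 to 24 hours after harvest. The cells are judged against acceptance criteria at the end of culture and infused about 24 to 48 hours after busulfan. Each child is therefore conditioned before release is decided. A harvest that yields too few cells is different: Protocol 7.3 withdraws that child without busulfan. The replacement rule in 9.12 covers both situations, but only release failure after busulfan is at issue here.

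**Where that child would be counted.**

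| Output | Rule | Child included? |
|---|---|---|
| Disposition, exclusion listing | SAP 8.1.1: denominator is subjects enrolled; excluded subjects listed with reason | Yes |
| Withdrawal summary | SAP 8.1.2: denominator is subjects treated; listing gives time since infusion | Not in the denominator; time undefined |
| SAE and AE tables | SAP 7.2 and 8.4.1.1: treated set, clock starts at infusion | No |
| OS and EvFS | SAP 7.1: treated set | No |

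SAP 8.4.1.2 and 8.4.1.3 also list adverse events that occurred before infusion, and deaths. The text does not say whether this covers a child who is never infused.

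**EvFS events.** SAP 8.3.1.2 counts death, reinstitution of PEG-ADA and a second transplant; the protocol's third event is an allogeneic transplant. Protocol 6.4.1 stops PEG-ADA at day +30 only in children who received the final product. The child in question never stops it, so there is nothing to reinstitute, and the back-up cells are the child's own. Adding the child to the denominator would not by itself register a failure; a rule is needed.

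**The plan's own precision figures (Protocol 11.4).** These are 7% at 20/20 and 12% at 19/20, defined as the half-width of the two-sided exact 95% interval. The Clopper-Pearson limits for x successes in n are the 0.025 quantile of Beta(x, n − x + 1) and the 0.975 quantile of Beta(x + 1, n − x).
- 19/20: 75.1% to 99.9%, half-width 12.4%. This matches 12%.
- 20/20: lower limit 0.025^(1/20) = 83.2%, half-width (100 − 83.2)/2 = 8.4%.
- The stated 7% is obtained only with the full 5% in the one open tail: 0.05^(1/20) = 86.1%, half-width 6.96%.

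The two-sided limits are used below.

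**Illustration.** Assume that all 20 infused children are event-free and that k conditioned, non-infused children are kept and counted as EvFS failures. Neither the 20/20 nor k is given in the documents. The nearest reported result is 100% OS and EvFS in 18 evaluable patients at the March 2016 cut-off (Protocol 2.1.6.2).

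| k | EvFS | Exact 95% CI |
|---|---|---|
| 0 | 20/20 = 100% | 83.2 to 100% |
| 1 | 20/21 = 95.2% | 76.2 to 99.9% |
| 2 | 20/22 = 90.9% | 70.8 to 98.9% |
| 3 | 20/23 = 87.0% | 66.4 to 97.2% |

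The first such child lowers the estimate by 4.8 points and the lower limit by 7.0 points (83.2 − 76.2).

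**The case against.** The strongest reply is that a treated set suits the stated objective, since Protocol 3.1 asks about the safety of transplanting transduced cells. The controls are as-treated too: SAP 7.1 and 7.2 admit only patients who received HSCT, and SAP 8.3.1.1 starts their clock at transplant. This stands for efficacy, and it is a good reason to keep the infused set as primary there. It does not settle the safety definition, because busulfan is given under the protocol as part of the intervention.

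A reader might also infer several stronger things that the documents do not support.
- That the child disappears from all reporting. SAP 8.1.1 keeps the child in disposition and in the exclusion listing. Protocol 9.5.2 sends all SAEs to the sponsor and the DSMB whatever their cause. Protocol 9.10 collects survival, rescue HSCT and PEG-ADA status after withdrawal where available.
- That an EvFS event defined by the plan is being left out. The child remains on PEG-ADA and does not return to it, so counting a failure extends the definition.
- That the comparison with HSCT is tilted because HSCT lacks this risk. The documents do not say so, and control candidates who never reached transplant are equally absent.
- That results are in fact inflated. No count of conditioned, non-infused children is given.

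**Conclusion.** The point holds in a limited form. Every trial-arm analysis set requires OTL-101 infusion. A child who receives busulfan and whose product then fails release would therefore be outside every planned SAE, OS and EvFS rate, although traceable in disposition and in the exclusion listing. This follows from the definitions and needs no assumption.

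The size is unknown and could be zero. SAP section 2 gives 20 treated (19 at UCLA and one at the NIH), and neither document states how many were conditioned but not infused. The illustrative drop in the lower EvFS limit, from 83.2% to 76.2% for one child or 70.8% for two, rests on two assumptions: 20/20 success among the infused, and counting non-receipt of the product as failure.

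The change is worth making because it removes a selection from the primary safety endpoint at small cost. It is not evidence that the reported results are wrong.

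**What to change.** 1. In SAP 7.2 and Protocol 11.5.1, define the trial-arm safety population as all subjects who received protocol busulfan, whether or not OTL-101 was infused. Report the number not infused.
2. Amend SAP 8.4.1.1 and 8.4.1.2 so that AEs and SAEs are also tabulated from the start of busulfan. Widening the population alone would not work: a never-infused child has no infusion date, so none of that child's events would enter the tables. The same change brings in infused children's events between busulfan and infusion, which are now only listed.
3. Keep the infused set as primary for efficacy. Add one descriptive, single-arm sensitivity analysis of OS and EvFS in all busulfan-exposed subjects, with time zero at busulfan and failure to receive OTL-101 stated as an EvFS failure.

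The cost is SAP and protocol wording, a second set of AE and SAE tables, and one sensitivity table. There are two limits. Data after withdrawal may be sparse, since Protocol 9.10 promises only limited information where available and no special evaluations. The sensitivity set is also not symmetric with the HSCT controls, who enter only if transplanted, so it should not feed the formal comparison. Enrolment is closed (Protocol 2.1.6.2), so the sponsor should be able to establish the count now. If it is zero, the OS and EvFS counts are unchanged and the report should say so.

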8.1 Subject Disposition

8.1.1 Summary of Populations

Number (%) of subjects enrolled (signed informed consent), treated, and in efficacy and safety populations will be summarised for the OTL-101 treated and HSCT control groups. The denominator for the percentages will be the number of subjects enrolled.

Should any subjects be excluded from any of the analysis populations, a listing will be produced for these subjects noting the reason for exclusion.

8.1.2 Summary of Withdrawals

Number (%) of subjects who completed the study period will be summarised along with the reason for study withdrawal. The denominator for the percentages will be the number of subjects treated.

At the interim look and the primary analysis, the number (%) completing the designated follow-up period and ongoing in the study will also be summarized.

Should any subjects have withdrawn from the study, a listing will be produced for these subjects noting the reason for study withdrawal, and the time since infusion at withdrawal.

Final Version 4.0 Page 12 of 27

8.2 Demography and Baseline Characteristics

Demography and baseline characteristics will be summarised for the safety population.

8.2.1 Demography

Age in months for the OTL-101 treated subjects will be calculated as: 12*(date informed consent signed – date of birth)/365.25.

Age in months for the HSCT controls will be captured on the eCRF.

Age in months will be summarized for the OTL-101 treated and HSCT control groups. Sex, race, weight and height at screening will be summarised for the OTL-101 treated group.

8.2.2 Medical History

Medical history was collected on two forms in this study. Each will be summarised separately.

The number (%) of subjects reporting medical history categorized as normal / abnormal clinically non-significant (CNS) / abnormal clinically significant (CS) will be summarised by body system for the OTL-101 treated subjects. Should any subject have an abnormal evaluation with the clinical significance assessment missing, this will be categorized as "abnormal unknown clinical significance" and this category will be added to the summary.

For the skin examination, the number (%) of OTL-101 treated subjects with each of the following will be summarized:

- evidence of active malignant disease other than dermatofibrosarcoma protuberans (DFSP);
- evidence of DFSP expected to require anti-neoplastic therapy within the 5 years following the infusion of genetically corrected cells;
- evidence of DFSP expected to be life limiting within the 5 years following the infusion of genetically corrected cells.

In addition, the number (%) of OTL-101 treated subjects with each of the following will be summarized:

- evidence of active opportunistic infection;
- known sensitivity to busulfan;
- expected survival < 6 months;
- pregnant;
- major congenital anomaly.

In addition, the number (%) of subjects reporting medical history at screening in each category will be summarised for the OTL-101 treated and the HSCT control groups.

Final Version 4.0 Page 13 of 27

8.2.3 ADA Deficiency Diagnosis

Age at diagnosis in months will be calculated for the OTL-101 treated subjects as: 12*(date of diagnosis – date of birth)/365.25.

For the HSCT control groups, the age at diagnosis will be recorded on the eCRF.

Time since diagnosis in months will be calculated as:

12*(date of transplant - date of diagnosis)/365.25,

or, for HSCT control subjects for whom the dates were not recorded, as:

age in months at transplant - age in months at diagnosis.

Age at diagnosis, time since diagnosis and the value used to diagnose ADA deficiency will be summarized using descriptive statistics for the OTL-101 treated subjects. In addition, the number (%) of subjects with each of the following will be summarized:

- ADA deficient as determined by reference laboratory;
- with family history of 1st order relative with ADA deficiency and clinical and laboratory evidence of severe immunologic deficiency;
- with evidence of severe immunologic deficiency prior to institution of immune restorative therapy;
- with no healthy, medically eligible HLA-identical sibling with normal immune function who may serve as an allogeneic bone marrow donor.

Age at diagnosis and time since diagnosis will be summarized using descriptive statistics for the HSCT control groups. In addition, the number (%) of subjects with each method of diagnosis (DNA sequencing/ confirmed absence of <3% enzymatic activity) will be summarized.

8.2.4 Disease History

Number (%) of OTL-101 treated subjects with each of the following will be summarized:

- Peri-natal complications (Prematurity / Infection / Other);
- Method of diagnosis (Newborn screen / Family History / Infection / Other);
- Siblings (Yes [HLA-Matched] / Yes [HLA-Not Matched] / No);
- Matched unrelated donor (MUD)/cord search performed;
- Pulmonary Complications;
- Feeding History;
- Prior Surgery.

8.2.5 Cytogenetics

Cytogenetics will be assessed at screening and categorised as normal or abnormal, with normal results subcategorised as 46XX/46XY/Other.

Final Version 4.0 Page 14 of 27

The number (%) of OTL-101 treated subjects falling into each category for source (PBMCs, bone marrow, amniotic fluid), result (normal/abnormal), category of normal result (46XX/46XY/Other) will be summarised.

8.2.6 Viral PCR

The number (%) of OTL-101 treated subjects with positive/not detected HIV, hepatitis B, hepatitis C, CMV and parvovirus B19 will be summarised.

8.2.7 Coagulation Tests

Coagulation tests (prothrombin time, partial thromboplastin time and internal normalised ratio) will be evaluated at screening and pre-harvest for the OTL-101 treated subjects.

For each parameter, the actual value will be summarised at each visit using descriptive statistics.

Coagulation tests will be flagged against the normal range as low/normal/high. For each parameter, the number (%) of subjects with evaluations that were low/normal/high relative to the normal range will be summarised by visit.

8.2.8 Urinalysis

Urine protein results will be summarized by visit using the number (%) of OTL-101 treated subjects with results in each category (0, 1+, 2+, 3+, 4+) of urinallysis result. In addition, a shift table from Screening to Pre-Harvest will be produced.

8.2.9 Electrocardiogram (ECG)

An ECG will be taken at screening which will be categorized as normal/ abnormal, not clinically significant/ abnormal, clinically significant. The number (%) of subjects with evaluations falling into each category will be summarised. Should any subject have an abnormal evaluation with the clinical significance assessment missing, this will be categorized as "abnormal unknown clinical significance" and this category will be added to the summary.

8.2.10 Echocardiogram

An echocardiogram will be taken at screening which will be categorized as normal/abnormal, not clinically significant/abnormal, clinically significant. The number (%) of OTL-101 treated subjects with evaluations falling into each category will be summarised along with the number (%) of subjects with uncorrected congenital cardiac malformation with clinical symptomatology. Should any subject have an abnormal evaluation with the clinical significance assessment missing, this will be categorized as "abnormal unknown clinical significance" and this category will be added to the summary. Left ventricular ejection fraction will be summarised using descriptive statistics.

In addition, details of any clinically significant findings will be listed.

Final Version 4.0 Page 15 of 27

8.2.11 Chest X-ray

Study: NCT01852071 - UCLA Fresh

A chest x-ray will be taken at screening which will be categorised as normal/ abnormal, not clinically significant/ abnormal, clinically significant. The number (%) of OTL-101 treated subjects with evaluations falling into each category will be summarised. Should any subject have an abnormal evaluation with the clinical significance assessment missing, this will be categorized as "abnormal unknown clinical significance" and this category will be added to the summary. In addition, the number (%) of OTL-101 treated subjects with active cardiac disease, including clinical evidence of congestive heart failure, cyanosis, hypotension will be summarized.

